#### Risk scoring algorithm

Predictive factor	Before a cycle of chemotherapy
Baseline score	10
Impact of patient risk factors	
Patient < 60 age	+1
Expectation (anticipation) of nausea and/or vomiting	+1

CONFIDENTIAL

Confidential	MyRisk	Date: 05 February 2024
	Protocol	
	PROTOCOL NUMBER: IBA1160	Version: 5.1

Patient has a history of morning sickness during a previous pregnancy	+1
Patient is about to receive platinum or anthracycline chemotherapy	+2
Patient used non-prescribed antiemetics at home in the prior cycle	+3
Patient has nausea or vomiting in the prior cycle	+5
About to receive the 2 nd cycle	-5
About to receive ≥ 3 rd cycle	-6

VISIT 0 will be conducted within 2 weeks before chemotherapy administration on cycle 1 or alternatively on Day 1 of cycle 1.

- Verify Inclusion/exclusion criteria
- Collect the following information:
  - o Demographic data
  - o Primary cancer diagnosis
  - o Past and recent medical history
  - o Number of scheduled cycles
  - o Expected time between cycles
  - o Eastern Cooperative Oncology Group (ECOG) performance status (0, 1 and 2)
  - o Prior radiation therapy and site (within previous 3 months)
- Risk scoring algorithm will be calculated

RISK FACTORS (Risk scoring algorithm calculation)*	ADDITIONAL RISK FACTORS
Age	Gender
Expectation of nausea and/or vomiting (YES/NO)	Weight
Morning sickness during previous pregnancy (YES/NO)	Duration of sleep the night before chemotherapy
Chemotherapy type (platinum or anthracycline chemotherapy) and chemotherapy regimen details	History of nausea and vomiting other than morning sickness in females (not-chemotherapy dependent, e.g., motion sickness or vestibular dysfunction)
Use of non-prescribed antiemetics by patients at home in the prior cycle (YES/NO)	Anticipatory nausea/vomiting (CINV before chemotherapy) (YES/NO)
Nausea and/or vomiting in the prior cycle (YES/NO)	Alcohol intake (number of units per week)
Cycle about to be received	Fatigue experience (symptom) (YES/NO)
	Smoking status (YES/NO)
	Anxiety over the last 24 hours (to be inquired right before chemotherapy) (YES/NO)

\* Non-naive patient treated outside the study with any chemotherapy regimen at the previous cycles (the next cycle starts 6 months or more later after the previous chemotherapy treatment was finished), will be screened with the following answers to the CINV algorithm questions:

Cycle of chemotherapy about to be received: 1st cycle

Patient used non-prescribed antiemetics at home in the prior cycle: no

Patient has nausea or vomiting in the prior cycle: no

### 3.6.3.2 VISIT 1: Day 1 of Cycle 1

The patients considered eligible at baseline and showing a risk score ≥ 13 will be randomized.

- WOCBP will perform a urine dipstick pregnancy test, to exclude pregnancy

CONFIDENTIAL

Confidential	MyRisk	Date: 05 February 2024
	Protocol	
	PROTOCOL NUMBER: IBA1160	Version: 5.1

- Complete the additional risk factor check inquiring "Anxiety over the past 24 hours (YES/NO) and "Duration of sleep the night before chemotherapy"
- Confirm eligibility of patients to chemotherapy as needed, according to the routine practice
- Administer the assigned antiemetic
- Administer chemotherapy at a due time after antiemetic is given
- Safety findings
- Supply the Patient's diary for cycle 1 and give instructions to the patient on how to fill it in from Day 1 to 5, and ask to bring it back on Day 1 of cycle 2
- Supply MAT for cycle 1, to be completed by the patient after 24 hours from chemotherapy administration and on Day 5 from chemotherapy administration, give instructions to the patient on how to fill it and ask to bring it back on Day 1 of cycle 2
- Supply FLIE for cycle 1, to be completed by the patient on Day 6 from chemotherapy administration (i.e., collection of data on nausea and vomiting from day 1 to day 5 from chemotherapy dosing), give instructions to the patient on how to fill it in and ask to bring it back on Day 1 of cycle 2
- Call patient between day 3 and 5 from chemotherapy to assess he/she is filling in the daily Patient's diary

### 3.6.3.3 VISIT 2: Day 1 of Cycle 2

- WOCBP will perform a urine dipstick pregnancy test, to exclude pregnancy
- Confirm eligibility of patients to chemotherapy according to the routine practice
- Check changes of the following screening visit parameters for the algorithm re-calculation:
  - o Expectation of nausea and/or vomiting YES/NO
  - o Chemotherapy regimen details
  - o Use of non-prescribed antiemetics at home in the prior cycle
  - o Nausea and/or vomiting in the prior cycle
  - o Number of cycles received
- Confirm the status of the added risk factors:
  - o Anticipatory nausea and/or vomiting in the prior cycle (YES/NO)
  - o Fatigue experience (symptom) YES/NO
  - o Duration of sleep during the night before chemotherapy
  - o Anxiety over the past 24 hours YES/NO
- Administer the assigned antiemetic
- Administer chemotherapy at a due time after antiemetic is given
- Safety findings (from diaries and inquiry)
- Rescue medications related to nausea and/or vomiting (from diaries and inquiry)
- Collect chemotherapy delay and/or dose reduction
- Collect and review the Patient's diary of cycle 1 and digitalize the data in the eCRF
- Collect and review the MAT of cycle 1 and digitalize the data in the eCRF
- Collect and review the FLIE questionnaire relevant to cycle 1
- Supply Patient's diary for cycle 2 and give instructions to the patient on how to fill it in from Day 1 to 5, and ask to bring it back on Day 1 of cycle 3
- Supply MAT for cycle 2, to be completed by the patient after 24 hours from chemotherapy administration and on Day 5 from chemotherapy administration, give instructions to the patient on how to fill it and ask to bring it back on Day 1 of cycle 3
- Supply FLIE for cycle 2, to be completed by the patient on Day 6 from chemotherapy administration (i.e., collection of data on nausea and vomiting from day 1 to day 5 from chemotherapy dosing), give instructions to the patient on how to fill it in and ask to bring it back on Day 1 of cycle 3
- Call patient between day 3 and 5 from chemotherapy to assess he/she is filling in the daily Patient's diary

CONFIDENTIAL

Confidential	MyRisk	Date: 05 February 2024
	Protocol	
	PROTOCOL NUMBER: IBA1160	Version: 5.1

### 3.6.3.4 VISIT 3: Day 1 of Cycle 3

- WOCBP will perform a urine dipstick pregnancy test, to exclude pregnancy
- Confirm eligibility of patients to chemotherapy according to the routine practice
- Check changes of the following screening visit parameters for the algorithm re-calculation:
  - o Expectation of nausea and/or vomiting YES/NO
  - o Chemotherapy regimen details
  - o Use of non-prescribed antiemetics at home in the prior cycle
  - o Nausea and/or vomiting in the prior cycle
  - o Number of cycles received
- Confirm the status of the added risk factors:
  - o Anticipatory nausea and/or vomiting in the prior cycle (YES/NO)
  - o Fatigue experience (symptom) YES/NO
  - o Duration of sleep during the night before chemotherapy
  - o Anxiety over the past 24 hours YES/NO
- Administered assigned antiemetic
- Administer chemotherapy at a due time after antiemetic is given
- Safety findings (from diaries and inquiry)
- Rescue medications related to nausea and/or vomiting (from diaries and inquiry)
- Collect chemotherapy delay and/or dose reduction
- Collect and review the Patient's diary of cycle 2 and digitalize the data in the eCRF
- Collect and review the MAT of cycle 2 and digitalize the data in the eCRF
- Collect and review the FLIE questionnaire relevant to cycle 2
- Supply the Patient's diary for cycle 3 and give instructions to the patient on how to fill it in from Day 1 to 5, and ask to bring it back at the last visit on Day 5 of cycle 3 or before the start of the next programmed chemotherapy cycle
- Supply MAT for cycle 3, to be completed by the patient after 24 hours from chemotherapy administration and on Day 5 from chemotherapy administration, give instructions to the patient on how to fill it and ask to bring it back at the last visit on Day 5 of cycle 3 before the start of the next programmed chemotherapy cycle
- Supply FLIE for cycle 3, to be completed by the patient on Day 6 from chemotherapy administration (i.e., collection of data on nausea and vomiting from day 1 to day 5 from chemotherapy dosing), give instructions to the patient on how to fill it in and ask to bring it back at the last visit on Day 5 of cycle 3 or before the start of the next programmed chemotherapy cycle
- Call patient between day 3 and 5 from chemotherapy to assess he/she is filling in the daily Patient's diary

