### 3.4.4. Study termination

The end of the study for each patient is defined as the day of Visit 4. Visit 4 is a visit on Day 5 of Cycle 3 or before the start of the next programmed chemotherapy cycle. Visit 4 is the final visit of the study.

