### 3.6.3.5 FINAL VISIT (VISIT 4): DAY 5 OF CYCLE 3 or before the start of the next programmed chemotherapy cycle

- Verify the general health status of the patient according to clinical routine
- Safety findings (from diaries and inquiry)
- Rescue medications related to nausea and/or vomiting (from diaries and inquiry)
- Collect and review the Patient's diary of cycle 3 and digitalize the data in the eCRF
- Collect and review the MAT of cycle 3 and digitalize the data in the eCRF
- Collect and review the FLIE questionnaire relevant to cycle 3.

CONFIDENTIAL

Confidential	MyRisk	Date: 05 February 2024
	Protocol	
	PROTOCOL NUMBER: IBA1160	Version: 5.1

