## Appendix 1 Study Flow Chart

	Screening visit Visit 0	Day 1 Cycle 1 Visit 1	Day 1 Cycle 2 Visit 2	Day 1 Cycle 3 Visit 3	Day 5 Cycle 3 Final visit Visit 4
	Visit 0 can be alternatively included into Visit 1				
ENROLMENT					
Eligibility screen (risk score patients' pre- selection)	x				
Informed consent	x				
Inclusion/exclusion criteria	x				
Baseline form	x				
Final patients' selection	x				
Pregnancy test	x	x	x	x	
INTERVENTION					
Randomization		x			
Intervention A group		x	x	x	
Intervention B group		x	x	x	
ASSESSMENT					
Cycle 1 form		x			
Cycle 1 Patient's diary, MAT and FLIE forms given to patient		x			
Cycle 1 Patient's diary, MAT and FLIE collection and eCRF form completion			x		
Cycle 2 form			x		
Cycle 2 Patient's diary, MAT and FLIE forms given to patient			x		
Cycle 2 Patient's diary, MAT and FLIE collection and eCRF form completion				x	
Cycle 3 form				x	
Cycle 3 Patient's diary, MAT and FLIE forms given to patient				x	
Cycle 3 Patient's diary, MAT and FLIE collection and eCRF form completion					x

CONFIDENTIAL

Confidential	MyRisk	Date: 05 February 2024
	Protocol	
	PROTOCOL NUMBER: IBA1160	Version: 5.1

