#### Appendix 4 FLIE questionnaire (English version)

### Functional Living Index - Emesis PATIENT INSTRUCTIONS

In the following questionnaire you are asked to rate how much nausea and vomiting have affected your quality of life. The first set of 9 questions refers to nausea and the second set of 9 questions refers to vomiting. The questionnaire should take approximately 10 minutes or less to complete. Please read the instructions before you begin. Think carefully about each question because your answers may help to develop treatments that will improve the quality of life for future patients.

[figure not shown]
For each question, you will rate how much nausea (or vomiting) has affected an aspect of your quality of life during the past five days. Please focus on your experiences **over that time period**. We are interested in **your opinions**, not those of family members or friends. Your answers will remain confidential.

You must answer every question. Use a black ball point pen and press firmly so that your mark is clear.

[figure not shown]
If you are unsure of your answer or do not understand the question, read the question again carefully and make a vertical mark (|) on the line based upon your best understanding of the question. If you want to change your answer, please do the following: make a new vertical mark (|); draw an arrow to the correct mark; initial and date the correction.

Each question uses a visual analogue scale. Think about how you rate your feelings and place a vertical mark (|) on the line at a point corresponding to how much your nausea (or vomiting) has affected that aspect of your quality of life. **Please read the question carefully because in some questions, a "1" indicates no effect on your quality of life and in other questions a "1" indicates a great deal of an effect on your quality of life.** You may place your vertical mark (|) at any point along the line. Be sure that you make your vertical mark (|) so that it intersects the horizontal line. Do not circle a number. Use a single vertical mark (|) as shown below.

[figure not shown]

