The end of the study for each patient is defined as the day of Visit 4. Visit 4 is a visit on Day 5 of Cycle 3 or before the start of the next programmed chemotherapy cycle. Visit 4 if the final visit of the study.

After participation in the study, the patient will be treated according to the common clinical practice based on the physician's discretion.

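### Visit 4, the end of study, may fall on Day 5 of Cycle 3, before the Cycle 3 FLIE is due (Day 6) and before the 0-120 h window closes; patients seen on that day have a truncated Cycle 3

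*Protocol*

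**What the plan says.** **Visit 4.** Protocol 3.4.4: "Visit 4 is a visit on Day 5 of Cycle 3 or before the start of the next programmed chemotherapy cycle". The same choice of dates appears in Protocol 3.6.3 (Visit 4) and 3.6.3.5. SAP 7.3 repeats it and adds: "The end of the study for each patient is defined as the day of Visit 4". The column heading in Appendix 1 gives one date only: "Day 5 Cycle 3 Final visit Visit 4".

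**FLIE.** Protocol 3.6.3.4: "Supply FLIE for cycle 3, to be completed by the patient on Day 6 from chemotherapy administration". The same bullet has the patient "bring it back at the last visit on Day 5 of cycle 3 or before the start of the next programmed chemotherapy cycle". Protocol 3.6.3.5 lists among the Visit 4 tasks: "Collect and review the FLIE questionnaire relevant to cycle 3". Protocol section 7 also places the FLIE on the sixth day after chemotherapy. The form (Appendix 4) asks how nausea or vomiting "has affected an aspect of your quality of life during the past five days".

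**Diary, rescue use and the primary window.** The diary covers Days 1 to 5 (Protocol 3.6.2). Rescue use goes in the diary and the eCRF (3.4.3) and is also asked about at Visit 4 (3.6.3.5). The MAT has no rescue item (Appendix 3). Complete response requires no emesis and no rescue over 0-120 h from the start of chemotherapy (3.5).

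**Missing data.** Secondary endpoints use last observation carried forward; the primary endpoint uses multiple imputation (Protocol 8.4, SAP 9.4.1).

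**Follow-up.** Adverse events are collected to the end of study (Protocol 10.3), and resource use for the duration of the study (3.7).

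**The concern.** One of the two permitted dates for the final visit comes before a form that the visit must collect, and before the primary observation window has closed. Neither document provides for forms to be returned after Visit 4.

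This is specific to Cycle 3. Cycle 1 and 2 forms come back on Day 1 of the next cycle, well after Day 6.

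Three things are at stake for patients seen on Day 5:

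- The Cycle 3 FLIE, a listed secondary endpoint, covers a different period from Cycles 1 and 2 or is replaced by the Cycle 2 score.
- A patient with no failure up to the visit who first takes rescue medication afterwards may not be recognised as a Cycle 3 failure.
- Cycle 3 adverse events and resource use are observed for a length of time that depends on when the site books the visit, in an open-label trial.

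**Working it through.** **1. Dates side by side (Cycle 3, Day 1 = day of chemotherapy)**

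- Visit 4, earliest permitted date: Day 5.
- Diary: runs through the end of Day 5.
- Primary window: closes at 120 h, the nominal end of Day 5.
- FLIE: due on Day 6.

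A Day 5 visit precedes the FLIE by at least one calendar day. Counting the FLIE day from chemotherapy as Day 0, as the wording of Protocol section 7 might suggest, moves it later and does not remove the conflict.

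**2. Unobserved hours**

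Nominally Day 1 is 0-24 h, so Day 5 is 96-120 h. The largest gap is 120 − 96 = 24 h. That is 24/120 = 20% of the overall window and 24/96 = 25% of the delayed phase.

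Real clock times shift this. Hours at visit = 96 + (visit clock time − chemotherapy start time). The documents give no clock times; I assume starts between 08:00 and 16:00 and visits between 09:00 and 17:00.

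- Start 08:00, visit 17:00: 105 h, gap 15 h (15/96 = 16% of the delayed phase).
- Start 16:00, visit 09:00: 89 h, gap 31 h (31/96 = 32%).

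These are shares of hours, not of events.

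**3. FLIE filled in at a Day 5 visit**

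At a nominal 96 h the patient has had four post-chemotherapy days, not five (96/120 = 80%). Five-day recall then reaches back before chemotherapy and omits the rest of Day 5.

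**4. Power**

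First the plan's own figure (Protocol 8.2, SAP 9.2): 71% v 60%, correlation 0.5, availability by cycle o = {1, 0.925, 0.85}, pairwise independent.

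- Design factor = [Σo + 0.5·Σ(j≠k) o_j·o_k] / (Σo)² = (2.775 + 2.561)/7.701 = 0.693.
- Logit scale: V = 1/(0.71·0.29) + 1/(0.60·0.40) = 9.023; d = 0.490.
- N = 2·(1.960 + 0.842)²·9.023·0.693/0.490² ≈ 409. The stated 410 is reproduced, with power 80.1%.

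Now remove a share of the otherwise available Cycle 3 primary outcomes, treating the loss as ignorable, at N = 410:

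- 10% removed: 79.5%
- 25% removed: 78.7%
- 50% removed: 77.4%
- 100% removed: 75.9%

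**5. How to treat Day 5 attenders (illustration)**

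Assume 100 patients, true Cycle 3 complete response 60%, half seen on Day 5 independently of outcome, and 38% of those already failed by the visit.

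- Seen later: 30 responders, 20 failures.
- Seen on Day 5: 19 recorded failures, 31 with no failure so far (30 true responders, 1 late failure).
- Score the 31 as responders: (30 + 31)/100 = 61%.
- Set only the 31 to missing: 30/(50 + 19) = 43%.
- Drop Cycle 3 for all 50 Day 5 attenders: 30/50 = 60%.

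Deleting apparent responders does far more damage here than the late failure it is meant to handle, because missingness then depends on the outcome.

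**The case against.** **The later option exists.** Both documents let Visit 4 take place at any time up to the next cycle. SAP 7.2 labels it a follow-up visit at the end of Cycle 3, and Protocol 3.6.2 has the FLIE completed at the end of each cycle. A site that books late has no conflict. This stands, and the harm is conditional. It does not remove the point: Day 5 remains permitted, it is the only date in the flow chart, and a patient whose chemotherapy ends at three cycles has no next cycle to define the later option.

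**Rescue use is not recorded only in the diary.** A reader might infer that it is, because the MAT has no rescue item. The eCRF and inquiry at Visit 4 are sources too. But on Day 5 none of the three can cover hours that have not yet happened.

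**Later return of forms is not forbidden.** A reader might infer that nothing can come back after Visit 4. The documents are silent. Site payment depends on complete three-cycle data including FLIE (Protocol 14), and the SAP requires the forms to be digitalised and checked before analysis (SAP 3). Both encourage full collection, but neither gives a route for it.

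**A blank Day 5 is not scored as a response.** A reader might infer that a late failure is counted as a complete response. No rule says so, and missing primary data go to multiple imputation. What is absent is any rule for a partly observed cycle.

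**Other limits.** The MAT delayed page is due four days after chemotherapy in every cycle, so its shortfall against 120 h is not caused by Visit 4. FLIE is a secondary, supportive endpoint. One visit rule applies to both arms, and no difference between arms in visit timing is shown.

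**Conclusion.** The contradiction is real and explicit. A permitted date for the final visit makes the Cycle 3 FLIE impossible on schedule and closes observation before 120 h.

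Its size depends on the share of patients seen on Day 5, which the documents do not give (0 to 100%). For those patients:

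- the Cycle 3 FLIE is early or missing;
- nominally up to 24 h (20%) of the Cycle 3 primary window is unobserved for rescue use, or 15 to 31 h under the assumed clinic hours;
- Cycle 3 adverse-event and resource follow-up is about 5 days, against up to about 21 days for a late visit if cycles last three weeks (an assumption).

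The documents do not support saying that Cycle 3 data are lost for everyone, that late failures are certainly scored as responses, or that the primary comparison is biased in a known direction. Only a patient whose first failure falls after the visit can be misclassified, and the number of such patients cannot be estimated from the documents. The sample size is not in question; the issue is systematically incomplete observation in one of three scheduled cycles.

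**What to change.** **Wording.** In Protocol 3.4.4, 3.6.3 (Visit 4), 3.6.3.4, 3.6.3.5 and Appendix 1, and in SAP 7.3, set Visit 4 on or after Day 6 of Cycle 3, at least 120 h after the start of chemotherapy and after the FLIE has been completed, and before any next cycle.

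**Patients already seen on Day 5.** Add to the SAP:

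- Flag each Cycle 3 FLIE completed before Day 6, and show the FLIE result with and without those forms.
- Report by arm how many Cycle 3 primary outcomes were observed for less than 120 h.
- Add a primary-endpoint sensitivity analysis whose exclusions do not depend on the observed outcome, for example dropping Cycle 3 for all Day 5 attenders whether or not they failed. Do not set only apparent responders to missing.
- Summarise Cycle 3 adverse events and resource use over a common period from dosing, alongside the planned summaries.

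**Cost.** A wording amendment to both documents and a few extra tables. The final visit moves by at least one day for some patients, with no added visit or procedure. The example sensitivity analysis assumes that visit date is unrelated to outcome. It would have at worst about 76% power if everyone had been seen on Day 5.

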### 3.6.3.5 FINAL VISIT (VISIT 4): DAY 5 OF CYCLE 3 or before the start of the next programmed chemotherapy cycle

- Verify the general health status of the patient according to clinical routine
- Safety findings (from diaries and inquiry)
- Rescue medications related to nausea and/or vomiting (from diaries and inquiry)
- Collect and review the Patient's diary of cycle 3 and digitalize the data in the eCRF
- Collect and review the MAT of cycle 3 and digitalize the data in the eCRF
- Collect and review the FLIE questionnaire relevant to cycle 3.

CONFIDENTIAL

Confidential	MyRisk	Date: 05 February 2024
	Protocol	
	PROTOCOL NUMBER: IBA1160	Version: 5.1

## 3.7. Health Economics Outcome Research (HEOR) Assessments

The health economic component described in this clinical protocol will only focus on resource utilisation linked to CINV and treatment of events (efficacy/safety).

To capture event-related resource utilisation, patients will be followed for the duration of the study. If one of the following events occurs; death, withdrawal of consent, or lost to follow up, resource utilisation for these patients will be reported up to the point they are withdrawn.

### 3.7.1. Resource Utilisation and Costs

The economic data will be collected primarily in physical units of health care resources used per patient and per event (efficacy/safety). The health economic endpoints are reported in section 3.5. Study endpoints.

Health resource utilisation will be collected for all patients participating in the clinical trial while resource costing, with costs collected outside the clinical study, will be performed in selected countries. No direct patient cost will be requested from institutions or patients.

